6.1.4 Adverse Event Collection Period

All AEs reported from the time of study drug administration until 30 days, following discontinuation of study drug administration have elapsed, whether solicited or spontaneously reported by the subject. AEs will be collected from the time of study drug administration until completion of this study. In addition, SAEs and protocol-related non-SAEs will be collected from the time the subject signed the study-specific informed consent.

AE information will be collected as shown in [Figure 3](#).

Figure 3. Adverse Event Collection

Additionally, in order to assist the adjudication process, additional information on any potential MACE will be collected, if applicable.

In the case of any of the following reported events, an appropriate supplemental MACE eCRF should be completed:

- Cardiac events;
- Myocardial infarction or unstable angina;
- Heart failure;
- Cerebral vascular accident and transient ischemic attack;
- Cardiovascular procedures (SAE Supplemental Procedure eCRF).

In the case of certain AEs, the corresponding supplemental AE eCRF should be completed:

- Hepatic;
- Renal;
- Herpes Zoster Infection;
- CPK increases considered by the investigator to be an AE.

6.1.5 Serious Adverse Event

In the event of a SAE, whether associated with study drug or not, the Investigator will notify Clinical Pharmacovigilance within 24 hours of the site being made aware of the SAE by entering the SAE data into the electronic data capture (EDC) RAVE[®] system. SAE that occur prior to the site having access to the RAVE[®] system or if RAVE is not operable can be Emailed (this is the preferred route) or faxed to Clinical Pharmacovigilance within 24 hours of being made aware of the SAE.

Email:	[REDACTED]
FAX to	[REDACTED]

For safety concerns, contact the Immunology Safety Team at:

Immunology Safety Team
[REDACTED]
[name]
[name]

Phone: [REDACTED]
Email: [REDACTED]

For any subject safety concerns, please contact the AbbVie Therapeutic Area Scientific Director listed below; who will discuss with the AbbVie Medical Director as needed.

In emergency situations involving study subjects when the primary Therapeutic Area Scientific Director is not available by phone, please contact the 24-hour AbbVie Medical Escalation Hotline where your call will be re-directed to a designated backup AbbVie Therapeutic Area Medical Director:

Phone: [REDACTED]

The sponsor will be responsible for Suspected Unexpected Serious Adverse Reactions (SUSAR) reporting for the Investigational Medicinal Product (IMP) in accordance with Directive 2001/20/EC. The reference document used for SUSAR reporting in the EU countries will be the most current version of the Investigator's Brochure for ABT-494 (upadacitinib).

In Japan, the principal investigator will provide documentation of all SAEs to the Director of the investigative site and the Sponsor.

6.1.6 Pregnancy

Pregnancy in a study subject must be reported to AbbVie within 1 working day of the site becoming aware of the pregnancy. Subjects who become pregnant during the study must be discontinued (Section 5.4.1).

Information regarding a pregnancy occurrence in a study subject or the partner of an enrolled subject and the outcome of the pregnancy will be collected. Pregnancies in study female subjects and female partners of male subjects will be collected from the date of the first dose through 30 days following the last dose of study drug.

Pregnancy in a study subject is not considered an AE. However, the medical outcome of an elective or spontaneous abortion, stillbirth or congenital anomaly is considered a SAE and must be reported to AbbVie within 24 hours of the site becoming aware of the event.

Subjects and their partners should avoid pregnancy throughout the course of the study, starting with the Screening Visit through 30 days after the last study drug administration

for female subjects and through 30 days after the last study drug administration for male subjects. Male subjects should refrain from donating sperm for up to 30 days post last dose of study drug. Results of a positive pregnancy test or confirmation of a pregnancy will be assessed starting with the Screening Visit through the final study visit. In the event of pregnancy occurring in the partner of an enrolled subject, written informed consent for release of medical information from the partner must be obtained prior to the collection of any pregnancy-specific information and the pregnancy will be followed to outcome.

6.1.7 Toxicity Management

The toxicity management of the AEs including AEs of special interest consists of safety monitoring (review of AEs on an ongoing basis, and periodical/ad hoc review of safety issues by a safety data monitoring committee), interruption of study drug dosing with appropriate clinical management if applicable, and discontinuation of the subjects from the study drug. The management of specific AEs and laboratory parameters is described below.

For subjects who discontinued study drug but continued study participation and are on standard of care therapies, these toxicity management requirements do not apply (including alerts from the central lab) and any intolerability to standard of care therapies should be managed by the prescribing physician.

Serious Infections: Subjects should be closely monitored for the development of signs and symptoms of infection during and after treatment with study drug. Study drug should be interrupted if a subject develops a serious infection or an opportunistic infection. A subject who develops a new infection during treatment with study drug should undergo prompt diagnostic testing appropriate for an immunocompromised subject. As appropriate, antimicrobial therapy should be initiated, and the subject should be closely monitored. Re-challenge with study drug may occur once the infection has been successfully treated. If study drug has been interrupted for more than 14 consecutive days in Period 1 or more than 21 consecutive days in Period 2, the subject must be

discontinued from the study drug. Subjects who develop active TB must be discontinued from the study drug.

Serious Gastrointestinal Events: Subjects presenting with the onset of signs or symptoms of a serious gastrointestinal event should be evaluated promptly for early identification of gastrointestinal perforation. If the diagnosis of gastrointestinal perforation is confirmed, the subject must be discontinued from the study drug.

Cardiovascular Events (MACE): Subjects presenting with potential cardiovascular events should be carefully monitored. These events will be reviewed and adjudicated by an independent Cardiovascular Adjudication Committee in a blinded manner.

Malignancy: Subjects who develop malignancy other than NMSC or carcinoma in-situ of the cervix must be discontinued from the study drug. Information including histopathological results should be queried for the confirmation of the diagnosis.

ECG Abnormality: Subjects must be discontinued from study drug for an ECG change considered clinically significant OR a confirmed absolute QTcF value > 500 msec.

Management of Select Laboratory Abnormalities: For any given confirmed laboratory abnormality (confirmation by repeat testing with a new sample), the Investigator should assess the subject, apply the standard of care for medical evaluation and treatment following any local guidelines. Specific toxicity management guidelines for abnormal laboratory values are described in [Table 6](#) and may require an appropriate supplemental eCRF be completed.

Table 6. Specific Toxicity Management Guidelines for Abnormal Laboratory Values

Laboratory Parameter	Toxicity Management Guideline
Hemoglobin	
 • If hemoglobin < 8 g/dL interrupt study drug dosing and confirm by repeat testing with new sample • If hemoglobin decreases \geq 3.0 g/dL from baseline, without an alternative etiology, interrupt study drug dosing and confirm by repeat testing with new sample. • If hemoglobin decreases \geq 3.0 g/dL from baseline and an alternative etiology is known, the subject may remain on study drug at the investigator's discretion. • If confirmed, continue to withhold study drug until hemoglobin value returns to normal reference range or its baseline value.
Absolute neutrophil count (ANC)	
 • If confirmed < 1000/μL by repeat testing with new sample, interrupt study drug dosing until ANC value returns to normal reference range or its baseline value. • Discontinue study drug if confirmed < 500/μL by repeat testing with new sample.
Absolute lymphocyte counts (ALC)	
 • If confirmed < 500/μL by repeat testing with new sample, interrupt study drug dosing until ALC returns to normal reference range or its baseline value.
Total white blood cell count	
 • If confirmed < 2000/μL by repeat testing with new sample, interrupt study drug dosing until white blood cell count returns to normal reference range or its baseline value.
Platelet count	
 • If confirmed < 50,000/μL by repeat testing with new sample, interrupt study drug dosing until platelet count returns to normal reference range or its baseline value.

Table 6. Specific Toxicity Management Guidelines for Abnormal Laboratory Values (Continued)

Laboratory Parameter	Toxicity Management Guideline
AST or ALT	
 • Discontinue study drug if confirmed ALT or AST $> 3 \times$ ULN by repeat testing with new sample and either total bilirubin $> 2 \times$ ULN or international normalized ratio > 1.5 
 ○ INR will only be measured in subjects with ALT or AST $> 3 \times$ ULN by the central lab by reflex testing and confirmation is not needed for consideration in toxicity management criteria. • Discontinue study drug if confirmed ALT or AST $> 3 \times$ ULN by repeat testing with new sample along with appearance of fatigue, nausea, vomiting, right upper quadrant pain or tenderness, fever, rash, and/or eosinophilia ($> 5\%$). • Discontinue study drug if confirmed ALT or AST $> 8 \times$ ULN by repeat testing with new sample. • Discontinue study drug if confirmed ALT or AST $> 5 \times$ ULN by repeat testing with new sample for more than 2 weeks. 
For all of the above ALT or AST elevation scenarios, complete supplemental hepatic eCRF.

Serum Creatinine	
 • If serum creatinine is $> 1.5 \times$ the baseline value and $> \text{ULN}$, repeat the test for serum creatinine (with subject in an euvolemic state) to confirm the results. If the results of the repeat testing still meet this criterion then interrupt study drug and re-start study drug once serum creatinine returns to $\leq 1.5 \times$ baseline value and $> \text{ULN}$. • If confirmed serum creatinine $\geq 2.0 \text{ mg/dL}$, interrupt study drug and re-start study drug once serum creatinine returns to normal reference range or its baseline value. 
For the above serum creatinine elevation scenarios, complete supplemental renal eCRF.

Creatine Phosphokinase	
 • If any confirmed CPK value $\geq 4 \times \text{ULN}$ (if symptomatic or asymptomatic), complete supplemental CPK eCRF. • If confirmed CPK $\geq 4 \times \text{ULN}$ accompanied by symptoms suggestive of myositis or rhabdomyolysis, interrupt study drug, complete supplemental CPK eCRF, and contact the AbbVie Therapeutic Area Scientific Director who will discuss with the AbbVie Medical Director.

For allowed study drug interruption, the following rules apply:

- For ABT-494/placebo (daily dosing):

- Allow study drug interruption up to ≤ 14 consecutive days for AEs and emergency surgery during Period 1.
- In Period 2 (after Week 16), study drug interruption due to AEs/surgery is allowed ≤ 21 consecutive days.
- Elective surgery during Period 1 (up to Week 16) is not allowed. Elective surgery during Period 2 only up to the Week 40 visit is discouraged and needs to be discussed with the AbbVie Therapeutic Area Scientific Director who will discuss with the AbbVie Medical Director. If the subject undergoes elective surgery, the study drug should be interrupted 1 week prior to the planned surgery. If the subject must undergo emergency surgery, the study drug should be interrupted at the time of the surgery. After emergency surgery, allow reintroduction of study drug once the physician has examined the surgical site and determined that it has healed and there is no sign of infection.

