 14. History of an allergic reaction or significant sensitivity to constituents of the study drugs and/or other products in the same class.
 15. History of clinically significant (per Investigator's judgment) drug or alcohol abuse within the last 6 months preceding the Baseline Visit.
 16. Female subject who is pregnant, breastfeeding or is considering becoming pregnant during the study or for approximately 30 days after the last dose of study drug.

17. Male subject who is considering fathering a child or donating sperm during the study or for approximately 30 days after the last dose of study drug.
18. Laboratory values meeting the following criteria within the Screening period prior to the first dose of study drug (Baseline Visit):
 - Serum aspartate transaminase (AST) $> 2 \times$ ULN;
 - Serum alanine transaminase (ALT) $> 2 \times$ ULN;
 - Estimated glomerular filtration rate (GFR) by simplified 4-variable Modification of Diet in Renal Disease (MDRD) formula < 40 mL/min/1.73 m²;
 - Total white blood cell count (WBC) $< 2,500/\mu\text{L}$;
 - Absolute neutrophil count (ANC) $< 1,500/\mu\text{L}$;
 - Platelet count $< 100,000/\mu\text{L}$;
 - Absolute lymphocyte count $< 800/\mu\text{L}$;
 - Hemoglobin < 10 g/dL.
19. Consideration by the Investigator, for any reason, that the subject is an unsuitable candidate to receive ABT-494 (upadacitinib) or participate in this study.
20. For subjects in Japan only: Positive result of beta-D-glucan (screening for pneumocystis jiroveci infection).

Rationale for Exclusion Criteria

1 – 7, 9	To select the appropriate subject population
8, 10 – 15, 18 – 20	To ensure safety of the subjects throughout the study
16, 17	ABT-494 is teratogenic in both rats and rabbits. The impact of ABT-494 on pregnancies is unknown

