6.1.1 Definitions

6.1.1.1 Adverse Event

An AE is defined as any untoward medical occurrence in a patient or clinical investigation subject administered a pharmaceutical product and which does not necessarily have a causal relationship with this treatment. An AE can therefore be any unfavorable and unintended sign (including an abnormal laboratory finding), symptom, or disease temporally associated with the use of a medicinal (investigational) product, whether or not the event is considered causally related to the use of the product.

Such an event can result from use of the drug as stipulated in the protocol or labeling, as well as from accidental or intentional overdose, drug abuse, or drug withdrawal. Any worsening of a pre-existing condition or illness is considered an AE. Worsening in severity of a reported AE should be reported as a new AE. Laboratory abnormalities and changes in vital signs are considered to be adverse events only if they result in discontinuation from the study, necessitate therapeutic medical intervention, meets protocol specific criteria (see Section 6.1.7 regarding toxicity management) and/or if the investigator considers them to be AEs.

An elective surgery/procedure scheduled to occur during a study will not be considered an AE if the surgery/procedure is being performed for a pre-existing condition and the surgery/procedure has been pre-planned prior to study entry. However, if the pre-existing condition deteriorates unexpectedly during the study (e.g., surgery performed earlier than planned), then the deterioration of the condition for which the elective surgery/procedure is being done will be considered an AE.

Expected manifestations of AD (i.e., itching, excoriations, oozing, crusting, erythema, etc.) should not be reported as AEs unless considered to be a worsening of the underlying disease.

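### The first creatinine restart rule in Table 6 requires a value above ULN: read literally, no normal value permits restart, and for baselines up to two-thirds of ULN no value does

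*Protocol*

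**What the plan says.** The serum creatinine row of Table 6 (Protocol Section 6.1.7) has two bullets.

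- **First bullet.** The trigger reads "If serum creatinine is $> 1.5 \times$ the baseline value and $> \text{ULN". If a repeat test confirms it, drug is interrupted. The restart instruction is "re-start study drug once serum creatinine returns to $\leq 1.5 \times$ baseline value and $> \text{ULN".
- **Second bullet.** For a confirmed value of 2.0 mg/dL or more: "interrupt study drug and re-start study drug once serum creatinine returns to normal reference range or its baseline value".

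The haematology rows use the same restart target as the second bullet. For haemoglobin the text is "continue to withhold study drug until hemoglobin value returns to normal reference range or its baseline value"; the neutrophil, lymphocyte, white-cell and platelet rows have the same end point.

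The text introducing the table says that for a confirmed abnormality "the Investigator should assess the subject, apply the standard of care for medical evaluation and treatment following any local guidelines". At entry, exclusion criterion 18 (Section 5.2.2) bars "Estimated glomerular filtration rate (GFR) by simplified 4-variable Modification of Diet in Renal Disease (MDRD) formula < 40" mL/min/1.73 m² but sets no limit on creatinine itself. No other protocol section restates the first-bullet restart rule, and the SAP has no restart rule. Neither document gives a numerical ULN for creatinine.

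**The concern.** A restart rule should describe recovery from whatever stopped the drug. Here the 1.5 × baseline part is turned round, but the requirement to be above ULN is carried over from the trigger as it stood. The rule then asks for an abnormal creatinine before drug may be given again. No clinical reason is offered, and the neighbouring rules point the other way.

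This is an operative dosing rule for an organ function that Section 6.1.1.3 lists among the adverse events of special interest (renal dysfunction). A site that follows the text keeps a recovered subject off drug. A site that restarts on sensible grounds departs from the written rule, and Section 7.0 does not permit intentional departures except to remove an immediate hazard. Either way, handling may differ between sites.

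**Working it through.** The plan states no figure to reproduce; the check is on the inequalities. Let C be the current creatinine, B the subject's baseline and U the ULN.

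**Inputs** (Table 6, serum creatinine, first bullet)

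- Trigger: C > 1.5B and C > U, that is, C > max(1.5B, U).
- Restart as written: C ≤ 1.5B and C > U, that is, U < C ≤ 1.5B.

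**What follows for any U**

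1. Every qualifying value is above U, so no normal-range value qualifies at any baseline.
2. The restart set is empty exactly when 1.5B ≤ U, that is, B ≤ 2U/3. The boundary is included because the ULN inequality is strict.
3. For 2U/3 < B ≤ U, the set is not empty but lies wholly above U, so a full return to baseline does not qualify.
4. For B > U, return to baseline does qualify, because U < B ≤ 1.5B. Such baselines are possible, since entry is limited by GFR and not by creatinine.

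**Illustration.** Assume U = 1.2 mg/dL, with 1.0 to 1.3 as the range. The empty-set cut-off 2U/3 is 0.67, 0.80 or 0.87 mg/dL for U = 1.0, 1.2 or 1.3. At U = 1.2 (all in mg/dL):

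| B | Trigger: C above | Restart as written | Restart with ULN clause deleted |
|---|---|---|---|
| 0.6 | 1.20 | none | ≤ 0.90 |
| 0.7 | 1.20 | none | ≤ 1.05 |
| 0.8 | 1.20 | none | ≤ 1.20 |
| 0.9 | 1.35 | 1.20 < C ≤ 1.35 | ≤ 1.35 |
| 1.0 | 1.50 | 1.20 < C ≤ 1.50 | ≤ 1.50 |
| 1.2 | 1.80 | 1.20 < C ≤ 1.80 | ≤ 1.80 |
| 1.3 | 1.95 | 1.20 < C ≤ 1.95 | ≤ 1.95 |

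**Possible corrections**

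- *Delete the ULN clause* (C ≤ 1.5B). The set is never empty. It contains the as-written set, so it bars nothing allowed now. Return to baseline always passes, because B ≤ 1.5B.
- *Negate the trigger* (C ≤ 1.5B or C ≤ U). Return to baseline always passes, but the stated limit is loosened when B < 2U/3. With B = 0.6 and U = 1.2, restart is allowed at 1.2, and 1.2 / 0.6 = 2.0 × baseline.
- *Reverse the ULN sign* (C ≤ 1.5B and C ≤ U). A subject with B > U cannot restart even when back at baseline.
- *Use the second bullet's target* (normal range or baseline). This is stricter. At U = 1.2 it bars 1.20 < C ≤ 1.50 for B = 1.0, values that would not have triggered an interruption under the first bullet.

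**The case against.** **The sign may be an extraction error.** The point turns on one comparison sign near the end of a table cell read from PDF. A misread cannot be excluded. It is not shown either: the ≤ sign was read correctly earlier in the same sentence. This stands as a caveat and makes the source page the first thing to check.

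**Sites will see what is meant.** Table 6 is titled as guidelines, standard of care is invoked, and the neighbouring rows make the intent plain. This largely stands and is why the impact is rated minor. However, Section 6.1.7 also calls these rules requirements, waiving them only for subjects already off study drug, and the standard-of-care sentence supplies no other restart threshold. Any literal error withholds drug; it does not add exposure.

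**Stronger readings that the documents do not support.**

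- A reader might infer that the rule forces discontinuation. Section 6.1.1.1 counts a laboratory change as an adverse event if it "meets protocol specific criteria (see Section 6.1.7 regarding toxicity management"), and Section 6.1.7 limits interruptions to 14 "consecutive days for AEs and emergency surgery during Period 1" and to 21 in Period 2. But Section 5.5.4, which does require discontinuation after longer interruptions, exempts reasons listed in Section 6.1.7. Forced discontinuation is possible but not established.
- A reader might infer that the two creatinine bullets contradict each other, because for B ≤ U no value meets both restart conditions. That assumes both must hold together, which Table 6 does not say. The second bullet is naturally read as governing once a confirmed value reaches 2.0 mg/dL.
- A reader might infer a loss of power or bias at Week 16. The documents give no frequency for these events, and nothing in the sample size or primary analysis depends on this rule.

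**Conclusion.** The point holds as a wording error in a dosing rule. As extracted, the first creatinine bullet permits restart only for U < C ≤ 1.5B. No normal-range value qualifies, and for a baseline at or below two-thirds of ULN none does. These results are algebraic and need no assumed ULN; only the mg/dL figures rest on the assumed 1.2 (range 1.0 to 1.3).

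The practical effect is minor: some recovered subjects may be kept off drug without need, or sites may act inconsistently. How often cannot be estimated from the documents. The conclusion depends on the sign being in the source as extracted. If the source instead reads at or below ULN, the literal defect described here disappears, leaving only the smaller problem that a subject with a baseline above ULN could not restart on return to baseline.

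**What to change.** First check the sign against the source page. If it is as extracted, delete the ULN clause from the restart half of the first bullet, so that restart requires only creatinine at or below 1.5 × baseline. This keeps the stated limit, bars no value allowed as written, and lets every subject who returns to that limit restart.

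Optionally, add a clause that the second bullet governs restart once a confirmed value is 2.0 mg/dL or more. It would help for baselines above 1.33 mg/dL (2.0 / 1.5), where 1.5 × baseline exceeds 2.0.

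The looser alternative (at or below 1.5 × baseline, or at or below ULN) and the stricter one (normal range or baseline) each move the threshold. They are choices for the sponsor's medical team. The looser one matters for low baselines: with the deletion, a subject with B = 0.6 and U = 1.2 still waits for 0.90 or less, although 1.0 is a normal value.

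The cost is one clause in the next protocol amendment, with the ethics committee approval that Section 9.1 requires for amendments. No new data, procedures or analyses are needed.
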